#### Part 3: Quantifying indoor AQ and respiratory symptoms

This part of the study will recruit approximately 60 patients, aiming for an equal distribution of people with asthma and people with COPD. Any severity stage will be allowed. In a study of an air purifier in asthmatic children a 4% difference in PEFR variability was seen [5]; the study had power 80% and  $\alpha$ =0.05, and it was possible to detect this with 30 patients in each arm of a study. Consequently, we feel that 30 is a reasonable target per condition in an exploratory study of this nature in adults.

#### Visit 1: Screening and issue of monitoring device(s)

The informed consent form is signed at this baseline visit. All available information will be collected according to a structured case record form (CRF). Baseline data will be collected including Date of Birth, Sex, Race and ethnicity, Height, Weight, Respiratory Diagnosis, Date of Diagnosis, Severity of disease (clinician defined), Exacerbations in last 12 months, Hospital admissions due to respiratory disease in last 12 months, smoking history, including years as a smoker, year of start and quitting and pack years, working status including relevant occupational exposures and type of agent. Current medication will also be recorded. Consent will be taken to extract from the medical record the latest values for lung function and any relevant radiological results. A symptom questionnaire will be distributed to collect data, and patients with asthma will also receive a peak expiratory flow monitor (if they do not already have one) for conducting daily peak expiratory flow rate (PEFR).

The questionnaire will be delivered in an electronic format compatible with all major phone operating systems, and will utilize validated questionnaires, namely the Bronkotest® questionnaire for patients with COPD and the asthma control test (ACT) for patients with asthma. Those with asthma will also enter their PEFR. Importantly the Bronkotest® system has already been developed for use in an e-diary for another study running locally (a clinical trial, Colour-COPD, funded by NIHR). Adaptation to use ACT is required, but not challenging, and is included in the budget. The Bronkotest® questionnaire will take approximately two minutes to complete each day, while the ACT questionnaire will take around one minute to complete. Self-reported symptoms will be gathered every day over a minimum 2-week period, but if the data in parts 1 and 2 suggests it is required an extension to a period of up to 6-weeks will be considered. If this is required the PIS will be amended with the new timeframe and approval sought for this from ethics. E-diary collection has been shown to result in more complete data than paper forms and be less expensive overall as a result, thus is commonly used in modern respiratory trials. A paper version of the e-diary will be made available for those without a suitable device on which to collect data electronically.

The indoor air quality device will be a Plume Labs Flow 2. This air quality device has previously been used in research by the sponsor. If there is not an adequate amount of Flow 2 devices available an AirBeam or Purple Air PA-I-Indoor device may be used. All of these devices will collect data on PM10 and PM2.5 mass concentrations which will be stored on clouds and which are easily accessible for the research team. It will be installed in the location deemed most appropriate for gathering of data on exposure to indoor air, which we anticipate being their home, but will emerge from parts 1 and 2 of the study. However, the device is portable to allow collection of data in multiple locations, and if the patient is moving between locations information on their location will be gathered by self-reporting. The research team will have a contact number set up for any device issues, and will arrange any repairs needed during the study.

As an example, our preferred device, the Flow 2, is 12.5cm in height, 4 cm width, depth 3.5cm and a weight of 70g; with manufacture estimated median coefficient of correlation with static reference monitors at 96% for NO2 experiments, 69% for VOC experiments, 93% for PM1, 92% for PM2.5, and 88% for PM10 experiments [13]. The growth in development in low cost sensors has been rapid over the last decade, with the quality assurance (QA) and validation processes for low cost sensors also rapidly evolving [14]. The latest advice on QA for low cost sensors provided from the dedicated DEFRA webpage [14] and in related literature will be followed at the time of the study. The chosen low-cost sensor at the time of the study will be the one which provides the best accuracy and precision of those available.

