#### **Analysis**

Simple descriptive statistics will be used to delineate characteristics of the cohort, and the correlation between each pollutant measured by the indoor monitor and day to day symptoms, as determined by the total score on Bronkotest® or ACT. In addition, daily puffs of inhaled short acting treatment (salbutamol) and (asthma only) PEFR will also be examined for relationship to indoor AQ, using a similar correlation analysis. Other factors relating to indoor AQ within collected demographic and medical history data will also be reported using simple comparative statistics.

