#### Inclusion criteria

Either COPD or asthma, as defined by their referring/usual care clinician in the medical record. The same inclusion criteria apply across all 3 parts of the study. Participants in this study need to be over the age of 16 and able to give informed consent.

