#### Appendix 2 – Schedule of Procedures

Study part	Visit 1	Daily participation	Visit 2
1	Consent, interview	-	-
2	Consent, questionnaire	-	-
3	Consent, demographics, medical history, issue of AQ monitor	Daily symptoms	Collection of AQ monitor

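### Part 3 states no daily record of the patient's own smoking or vaping, so in current smokers and unidentified vapers the day-to-day pollutant–symptom association cannot be adjusted for what they inhaled that day

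*Protocol*

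**What the plan says.** The Visit 1 section of the protocol lists the baseline data. Smoking appears there as "smoking history, including years as a smoker, year of start and quitting and pack years". Every item named is constant within a patient over the monitoring period. Vaping and e-cigarettes are not mentioned in the protocol.

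The daily data stated for Part 3 are:

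- Symptoms: "Self-reported symptoms will be gathered every day over a minimum 2-week period", by Bronkotest in COPD and ACT in asthma.
- Reliever use and peak flow: the Analysis section says "daily puffs of inhaled short acting treatment (salbutamol) and (asthma only) PEFR will also be examined for relationship to indoor AQ".
- Location, conditionally: "if the patient is moving between locations information on their location will be gathered by self-reporting".

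In Appendix 2 the only Part 3 entry for daily participation is "Daily symptoms".

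Eligibility is broad. The disease criterion is "Either COPD or asthma, as defined by their referring/usual care clinician in the medical record", with an age limit and capacity to consent. The only exclusion is being unwilling or unable to take part. The Analysis section plans "the correlation between each pollutant measured by the indoor monitor and day to day symptoms" and gives baseline factors simple comparative statistics.

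**The concern.** A cigarette smoked indoors does two things on the same day: it raises the particle reading on the monitor, and it reaches the airways directly. The patient's own smoking is then a time-varying common cause of exposure and outcome. The opposite pattern is also plausible: on a bad day the patient smokes less, the reading falls, and the association is pushed down or reversed. Because the direction is unknown, the bias cannot be allowed for when the result is read.

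Pack years and start and quit years do not change from one day to the next, so they cannot adjust an association that does. A later analysis plan can choose a model, but it cannot recover a daily count that was never collected.

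Objective 2 seeks symptom outcomes driven by air quality. The Recruitment target section says Part 3 data would help power later interventional studies, and the Background cites air purifiers as one such intervention. Cleaning room air does not remove directly inhaled smoke, so an estimate that includes it is a less reliable guide to what such a study could show.

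**Working it through.** The protocol gives no figure on this point. Its Part 3 target of 30 per condition is used below only to count patient-days.

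**1. What could be used for adjustment.** Visit 1 gives a fixed smoking history. The daily record gives symptoms, salbutamol puffs, peak flow in asthma, and location when the patient moves about. No stated item varies by day and measures smoking or vaping. The quit year should, however, separate current from former smokers.

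**2. Spurious correlation within current smokers.** Suppose room air has no effect on symptoms and the day's own smoking drives both variables. Let a be the correlation of daily smoking with that day's PM, and b its correlation with that day's symptoms. The induced correlation is a × b. Neither value is in the protocol; both are assumptions.

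- Low: 0.3 × 0.2 = 0.06
- High: 0.5 × 0.3 = 0.15
- If b reaches 0.4: 0.5 × 0.4 = 0.20

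If b is negative, the signs reverse.

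**3. Pooled over all patients.** With a share q of smokers and equal within-patient variances in everyone, the pooled within-patient correlation is about q × a × b. The protocol does not state q, so it is ranged.

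| q | a×b = 0.06 | a×b = 0.15 | a×b = 0.20 |
|---|---|---|---|
| 10% | 0.006 | 0.015 | 0.020 |
| 20% | 0.012 | 0.030 | 0.040 |
| 40% | 0.024 | 0.060 | 0.080 |

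A simulation agrees within Monte Carlo error (60 patients × 14 days, patient-centred correlation, 300 replicates, a of 0.3 or 0.5, b of 0.2 or 0.4). Pooled values ran from 0.007 to 0.074, smokers' from 0.059 to 0.195, and non-smokers' from −0.006 to 0.001.

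**4. If smokers' PM varies more.** Assume the within-patient SD of PM is three times as large in smokers, with equal symptom SD. The pooled value becomes 3q × a × b / √(9q + 1 − q).

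- q = 20%: 0.6/√2.6 = 0.372; × 0.06 to 0.15 gives 0.022 to 0.056
- q = 40%: 1.2/√4.2 = 0.586; × 0.06 to 0.15 gives 0.035 to 0.088

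**5. Comparison with nominal significance.** Within-patient degrees of freedom are patients × 14 − patients − 1. Critical r (two-sided 0.05) is t/√(t² + df).

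- All 30 patients: 420 − 30 − 1 = 389 df, critical r about 0.099
- 6 smokers: 84 − 6 − 1 = 77 df, critical r about 0.22
- 12 smokers: 168 − 12 − 1 = 155 df, critical r about 0.157

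The smoker-only 0.06–0.15 must be set against the smoker-only thresholds, and the pooled values against 0.099. For smoker shares up to 40%, the induced correlation with b of 0.2–0.3 stays below the matching threshold.

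**The case against.** Several points on the other side have weight.

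- **Non-smokers are identifiable.** A reader might infer that Part 3 as a whole cannot separate inhaled smoke from room air. The documents do not support that. The quit year lets current smokers be distinguished, so an analysis in non-smokers is possible with the data already planned. This stands, except that vapers would sit unrecognised in that group.
- **The list is open.** The smoking items follow the word including, and the case record form is not shown. It might hold a current-amount or vaping item. The protocol states none, and the open baseline list would not supply a daily item in any case. This stands as a caveat.
- **The pooled bias is small.** A reader might set the smoker-only 0.15 against the 0.099 threshold for 30 patients and conclude that a false nominally significant result is likely. The two figures refer to different sets of patients, so that inference fails. This stands.
- **Indoor smoke is an indoor source.** Smoke released into the room falls within the study's aim; only the directly inhaled part confounds. This stands and shapes the remedy.
- **Part 3 is exploratory, and covariates belong in an analysis plan.** This holds for the choice of model but not for collection: without the diary item there is nothing to adjust for.

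The Analysis section also does not say whether its correlation is within patients. If it mixes in differences between patients, baseline history could help with that part, but not with the day-to-day part.

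**Conclusion.** The point holds in a limited form. The protocol states no daily record of own smoking or vaping and no vaping status at baseline, while it admits current smokers and plans a day-to-day correlation. The affected patients are current smokers and unidentified vapers, not known non-smokers.

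Under the assumed correlations, the distortion is about 0.06–0.15 in r, of either sign, within smokers. Pooled, it is roughly 0.01–0.06 at 10–40% smokers. It is somewhat higher if the smoking–symptom correlation reaches 0.4 or smokers' particle readings are more variable. All of this rests on correlations and a smoker share that the protocol does not give.

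No claim is made that the bias would reach nominal significance. Nor do the documents show that a later purifier study would be misled, since that would require smokers to dominate the estimate. This is a cheap improvement to data collection, best made before recruitment because the data cannot be recovered afterwards.

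**What to change.** 1. Add one line to the daily diary, electronic and paper: cigarettes, other tobacco and vaping today, and how many of these indoors, with zero for non-users.
2. Add current smoking amount and vaping status to the Visit 1 case record form and to the baseline list in the protocol. Add the diary item to Appendix 2.
3. In the Analysis section, report the day-level association in three ways: unadjusted, adjusted for the daily count, and separately in patients who neither smoke nor vape.

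The cost is a few seconds per diary day and two baseline items; the e-diary is already being adapted for the ACT. The non-user analysis will have fewer patients. Adjustment also removes some genuine exposure to smoke in the room, so the adjusted estimate should stand beside the unadjusted one and not replace it.

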Appendix 4 – Information about Air Quality Devices, in preferred order.

Name of Air	Basic Information	Preference	Additional	Image
Quality Device		of Use	Information	
Plume Labs Flow	Pollutants Measured: PM1,	First	- Not Weatherproof.	
2	PM2.5, PM10, NO2, VOCs		- Data is transferred	
Plume Labs - Flow	Size: 125mm x 40mm x 35mm		via Bluetooth (no	
2 (aqmd.gov)	Weight: 70g		data stored	
z (aqmu.gov)	Power Supply: USB Cable		internally.	
	Sampling Mechanism: Fan,		- 24-hour battery	Tracks.
	Laser Particle Counter		life.	2xt#
	(Particle Matter), Heated			
	Metal Oxide Sensor (Gases)			
	Price: £151.50 (14.04.2022)			
AirBeam	Pollutants Measured: PM1,	Second	- Temperature and	
	PM2.5, PM10		Relative Humidity	
AirBeam2	Size: 132mm x 98mm x 28mm		can also be	
Technical	Weight: 142g		measured.	
Specifications,	Power Supply: USB C Cable		- Data is transferred	
Operation &	Sampling Mechanism:		via Wi-Fi (no data	
Performance	Sensing Chamber		stored internally).	
(habitatmap.org)	Price: £189.50 (14.04.2022)		- 10-hour battery	
			life.	
December Aire DA I	Dellestante Maranente DMA2 F	The inval	Durana	
Purple Air PA-I-	Pollutants Measured: PM2.5	Third	- Pressure,	
Indoor	Size: 108mm x 67mm x 57mm		Temperature and	
PurpleAir PA-I-	Weight: N/A		Relative Humidity	
Indoor Air Quality	Power Supply: USB A Cable		can also be	
Sensor - PM2.5	Sampling Mechanism: Laser		measured.	
Detector	Particle Counter		- Indoor Use Only.	
= ======	Price: £151.50 (14.04.2022)		- Data is transferred	
			via wi-fi (no data is	
			stored (internally).	
				makes to the book of the control of

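### Nebulised treatment may register as particulate matter on the laser-counter monitors, and Part 3 records no nebuliser sessions with which to separate it from pollution

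*Protocol*

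**What the plan says.** - **Device.** Visit 1 of Part 3 names the Flow 2 as the monitor, with AirBeam or Purple Air as substitutes, and states: "All of these devices will collect data on PM10 and PM2.5 mass concentrations". (Appendix 4 lists only PM2.5 for the Purple Air; that is a separate discrepancy.)
- **Sensing principle.** Appendix 4 gives "Laser Particle Counter" for the particle channel of the Flow 2 and for the Purple Air. For the AirBeam it gives only "Sensing Chamber".
- **Place.** The monitor goes where exposure is judged most relevant, "which we anticipate being their home". It is portable, and no room is named.
- **Patients.** "Any severity stage will be allowed", and the exclusion criteria remove only those unwilling or unable to take part. Nebuliser users can therefore enter, although the protocol never mentions nebulisers.
- **Treatment data.** Current medication is recorded at baseline. The Analysis section uses daily salbutamol puffs. No count or timing of nebuliser sessions is described.
- **Analysis.** The plan is "the correlation between each pollutant measured by the indoor monitor and day to day symptoms", and a similar correlation of indoor air quality with salbutamol puffs. Reliever use appears only as an outcome, not as a possible source of particles.

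**The concern.** Inhaled treatment is delivered as a respirable aerosol. A counter that detects particles optically would not be expected to distinguish treatment droplets, or the residue they leave, from particles of any other origin. If a patient nebulises more on bad days near the monitor, the causal arrow runs from symptoms to the PM reading. That gives a positive association in the direction Part 3 sets out to explore. Comparing each patient with himself or herself does not help, because the mechanism works from day to day within the patient.

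Two things make this worth fixing in the protocol. First, session times that are not collected prospectively cannot be recovered later, so no statistical analysis plan could identify the affected readings. Second, the recruitment-target section says Part 3 data will support power calculations for later interventional studies. An inflated correlation would carry forward as an over-optimistic effect.

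**Working it through.** The protocol gives no figure for this artefact, so there is none to reproduce. Every physical input below is an assumption.

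**Step 1: PM added to the 24-hour mean by one nebuliser session**

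A well-mixed room with first-order particle loss gives c = M·f / (V·k·24).
- M = 25,000 µg non-volatile mass (2.5 mL of 0.9% saline plus drug)
- f = 0.1 to 0.4, the fraction that escapes into the room
- V = 30 to 60 m³
- k = 1 to 3 per hour

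Low end: 25,000 × 0.1 / (60 × 3 × 24) = 0.58 µg/m³. High end: 25,000 × 0.4 / (30 × 1 × 24) = 13.9 µg/m³. The range is 24-fold, and it counts all escaping mass as PM2.5.

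**Step 2: spurious within-patient correlation with no true effect**

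Let daily PM = B + c·D. B is background with standard deviation σ, independent of symptoms S (higher = worse), and D is sessions per day. Then r(PM,S) = ρ·κ/√(1+κ²), where κ = c·SD(D)/σ and ρ = corr(S,D).

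Assume 1 session on ordinary days and 3 on the worst 30% of days. Then SD(D) = 2·√(0.3 × 0.7) = 0.917. With normally distributed symptoms ρ = 0.76, which is a tight link between symptoms and treatment.

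| c (µg/m³ per session) | σ = 5 | σ = 10 | σ = 20 | σ = 5, ρ = 0.4 |
|---|---|---|---|---|
| 0.9 | 0.12 | 0.06 | 0.03 | 0.07 |
| 1.7 | 0.23 | 0.12 | 0.06 | 0.12 |
| 3.5 | 0.41 | 0.23 | 0.12 | 0.22 |
| 7 | 0.60 | 0.41 | 0.23 | 0.32 |

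Example: c = 3.5, σ = 5 gives κ = 3.5 × 0.917 / 5 = 0.64, and r = 0.76 × 0.64 / √(1 + 0.64²) = 0.41. Simulating 14-day records gives the σ = 5 and σ = 20 columns to within 0.01. The increments 0.9 to 7 lie inside the Step 1 range. At its two ends, with σ = 5 and ρ = 0.76, the formula gives 0.08 and 0.71. So 0.03 to 0.60 is a working range, not a bound.

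**Step 3: shift in the cohort average**

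Patients who do not nebulise contribute about zero. With σ = 5 and an assumed 10-30% nebulising, the shift runs from 0.10 × 0.12 = 0.01 to 0.30 × 0.60 = 0.18. It shrinks with a larger σ or a weaker ρ. For scale, 30 patients × 14 days = 420 person-days, treated as independent, have a two-sided 5% critical correlation of 0.096. The lower shift is well below that and the upper one above it.

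**Step 4: hand-held puffs in a room**

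Take 10 puffs as about 0.3 µg/m³ per day, added on the worst 30% of days, with σ = 5. Then κ = 0.3 × √(0.3 × 0.7) / 5 = 0.027 and r = 0.76 × 0.027 = 0.02, which is negligible.

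**Step 5: does adjusting for session count remove it?**

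In this model r(PM,D) = κ/√(1+κ²), so r(PM,S) − r(PM,D)·ρ = 0. The partial correlation is zero, and simulation gives 0.00 at every increment. Adjustment works, but only if sessions are recorded.

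**The case against.** The strongest case against has four parts.

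1. **The protocol never mentions nebulisers, and the reliever it does name is salbutamol by the puff, with a negligible effect in a room.** This stands as a limit on size. It does not remove the point, because the eligibility rules admit nebuliser users and set no severity limit.
2. **Cleaning readings and choosing sensitivity analyses commonly belong in the statistical analysis plan, and the protocol promises to follow current quality-assurance advice for low-cost sensors.** This stands for the analysis step. It does not reach the diary, since what is collected daily is a protocol decision and nothing later can replace it. The quality-assurance commitment, as written, does not mention a treatment log.
3. **The magnitude rests on favourable assumptions.** This stands. A looser treatment response roughly halves r, and at σ = 20 it is 0.03 to 0.23. Treatment on a fixed schedule adds only a constant offset, and treatment taken away from the monitor adds nothing.
4. **Part 3 is exploratory.** True, but its results are meant to feed later power calculations.

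A reader might go further and infer any of the following, none of which the documents support:
- That all three monitors count by laser. Appendix 4 does not say so for the AirBeam.
- That bad days do produce high PM readings. The protocol has no figure on nebuliser use or on device response to aerosol.
- That propellant or solvent trips the VOC sensor, or that a worn monitor is badly affected by puffs. Neither has a figure.
- That covariate adjustment cannot help. Step 5 shows that it can.
- That siting the monitor a couple of metres away would solve it. In the well-mixed room used for the magnitude, that changes nothing.

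**Conclusion.** The point holds as an uncontrolled possible artefact, not as a demonstrated bias. The documents establish each structural element: laser counters on the first- and third-choice devices, probable home placement, no severity limit, a PM-symptom correlation, and no described record of nebuliser sessions. That the counters register treatment aerosol is physical reasoning, not protocol text.

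Where patients nebulise more on bad days near the monitor, the bias runs towards more pollution, more symptoms. Its size is unknown. Among nebuliser users the assumptions above give a within-patient r of about 0.03 to 0.60. Across the cohort the shift is no more than about 0.01 to 0.18 if 10-30% nebulise, so it could be trivial or could be mistaken for a finding. The change is worth making because it is cheap and the missing data cannot be reconstructed afterwards.

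**What to change.** **Visit 1 (symptom diary).** Add one daily line for the number and clock times of any nebuliser sessions.

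**Analysis.** Add a sensitivity analysis of the PM-symptom correlation that (a) removes PM readings for a fixed, pre-stated window after each logged session before the daily value is formed, or adjusts for daily session count, and (b) is repeated without nebuliser users. The window is preferable to the adjustment. Sessions are a consequence of symptoms, so adjusting for them would also weaken a true effect of air on symptoms.

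Treatment is unchanged. The cost is one extra diary item for the minority who nebulise and some valid readings discarded, in the sensitivity analysis only.
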